Cost data: There will be two cost categories: *intervention costs* and *healthcare utilization costs*. Intervention costs will cover the costs incurred in the implementation of the intervention. This will include, for the HIWL arm, the provider visits (in-person and telemedicine) associated with the intervention will be assessed in terms of the insurance reimbursement (\$). For intervention services and resources not reimbursed by insurance (meals, software installation, staff time), we will use the micro-costing approach to aggregate the costs. As insurance reimbursement for the same service may vary by insurer, we will use Medicare fee-for-service reimbursement as the standardized rate so as to limit confounding arising from differences in insurer composition across intervention arms (ResDAC 2020). Patient out-of-pocket costs will also be included (e.g., insurance co-payments and deductibles). We will not include any costs relating to the research administration (e.g., staff time for data collection and analysis). For the HIWL+ CGM arm, we will include the cost of continuous glucose monitoring. Healthcare utilization costs will include healthcare services used during the study period but are not part of the interventions: hospitalizations, emergency department visits, outpatient visits, and prescription medications. Costs of these services will be assessed at Medicare rates. We will refer to the sum of the intervention and healthcare utilization costs as the *total costs*. Note that an intervention may lead to higher intervention costs compared to the control arm; however, if an intervention results in higher rates of diabetes remission, then healthcare utilization may be lower for the intervention cohort, compared to the control arm. The total cost captures the net change of the higher intervention and lower utilization costs.

Cost-effectiveness Outcomes: Our main outcome for cost-effectiveness analysis will be diabetes remission. We will compare the relative costs of achieving one additional remission using alternative interventions. As secondary outcomes, we will also examine the cost-effectiveness of (a) one percentage unit reduction in A1c and (b) one additional QALY.

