Cost-Effectiveness Analysis: The most commonly used measure of cost-effectiveness is the incremental cost-effectiveness ratio (ICER), defined as the ratio of between incremental costs (difference in total costs between intervention and control arms) and incremental diabetes remission (difference in the number of patients with remission in the intervention and control arms)³³. This measure is meaningful in contexts where an intervention increases total costs (since the denominator is expected to be positive, with higher diabetes remission in the intervention arm relative to the control arm). However, in our context where total costs include both intervention and non-intervention healthcare utilization, total costs for the intervention arm may be lower (e.g., if diabetes remission is accompanied by fewer emergency department visits or fewer medications). In this situation, we will report two measures: a) the average additional intervention cost for each additional diabetes remission achieved; and b) the average reduction in healthcare utilization cost for each additional diabetes remission achieved. For the secondary outcome of A1c reduction, we will similarly estimate the average cost of achieving one percentage point reduction in A1c and one additional QALY for each arm (Laiteerapong et al. . We will obtain 95% confidence interval of each estimate based on bootstrap resampling (Briggs et al. 1999). We will perform a variety of sensitivity analyses, including alternative healthcare reimbursement rates (e.g., 10 percent higher than Medicare rates).

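### The cost-effectiveness analysis costs A1c and QALY arm by arm instead of against DSME, and leaves the comparison, the choice of remission measure and the DSME cost items unclear

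*Combined protocol and SAP*

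**What the plan says.** The aim is comparative. Under Cost-effectiveness Outcomes, Section 8.1 states: "We will compare the relative costs of achieving one additional remission using alternative interventions". Remission is the main outcome there; A1c and QALY are secondary.

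Section 9.4.1 (Cost-Effectiveness Analysis) then sets these rules:

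- The ICER numerator is the "difference in total costs between intervention and control arms" and its denominator the "difference in the number of patients with remission in the intervention and control arms".
- The ICER is described as meaningful where the intervention raises total cost. The text adds that "total costs for the intervention arm may be lower" and goes on: "In this situation, we will report two measures". The two are the added intervention cost, and the utilization saving, per additional remission.
- For the secondary outcomes the plan will estimate "the average cost of achieving one percentage point reduction in A1c and one additional QALY for each arm".
- On precision: "We will obtain 95% confidence interval of each estimate based on bootstrap resampling". The type of bootstrap interval is not given.

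For intervention costs, Section 8.1 (Cost data) says: "This will include, for the HIWL arm, the provider visits (in-person and telemedicine) associated with the intervention". It then names meals, software installation and staff time as items to micro-cost, and adds glucose-monitor cost for HIWL + CGM. No item is named for DSME. Utilization costs are confined to services outside the interventions.

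The Section 3 table places the expenditure comparison under Tertiary/Exploratory.

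**The concern.** A cost-effectiveness ratio is useful when it says what one more unit of benefit costs compared with the alternative. An arm's own cost divided by its own change from baseline does not say this, because it credits the arm with improvement that would also have occurred under DSME and charges it with cost that DSME would also have incurred. It becomes unstable or negative when the arm's change is small, which is plausible for EQ-5D over 12 months and most of all in DSME.

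Three looser points sit beside this. If the sign of an observed cost difference selects the remission measure, chance can make the selection. Counts in place of proportions let group size enter the ratio once groups differ. And if DSME resources were recorded under neither cost category, incremental cost would be overstated by their full amount. Staff time that is not logged during the trial is hard to recover afterwards.

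**Working it through.** The cost-effectiveness plan states no numerical result, so there is no figure to reproduce. All dollar amounts and EQ-5D standard deviations below are assumptions. Remission rates are those that Section 2.2 reports for the cited meal-replacement trial: 46% v 4% at one year and 36% v 3% at two years. The A1c difference of 0.44 points is from the same section.

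**1. Per-arm average against increment**

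- A1c, assumed costs $13,000 and $10,000, assumed falls 1.00 and 0.56 points (difference 0.44). Per arm: 13,000/1.00 = $13,000 and 10,000/0.56 = $17,857 per point. Incremental: 3,000/0.44 = $6,818.
- QALY, assumed costs $6,000 and $2,000, assumed gains 0.05 and 0.03. Per arm, active: 6,000/0.05 = $120,000. Incremental: 4,000/0.02 = $200,000.

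The active arm's average lies above the increment in the first example and below it in the second. The error has no fixed direction, so a reader cannot correct for it.

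**2. Denominator of a per-arm QALY ratio**

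Section 8.1 takes the QALY change as the EQ-5D score at 12 months minus baseline. With n = 30, mean change m and SD s, the share of bootstrap means at or below zero is about Φ(−m / (s/√30)). For s = 0.15, s/√30 = 0.0274; for s = 0.20 it is 0.0365.

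| Mean change m | s = 0.15 | s = 0.20 |
|---|---|---|
| 0 | 50% | 50% |
| 0.02 | 23% | 29% |
| 0.03 | 14% | 21% |
| 0.05 | 3% | 9% |
| 0.10 | 0.01% | 0.3% |

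The problem is one of small changes. It disappears if the mean change is 0.10 or more.

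**3. Sign of the cost difference**

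Simulation: 600 trials per setting, 1,000 resamples each, 30 per arm, lognormal costs, DSME mean $10,000, coefficient of variation 1.

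| True cost difference | Observed difference negative | Bootstrap 95% interval for cost difference spans zero |
|---|---|---|
| $0 | about 49% | about 93% |
| $1,000 | about 36% | about 91% |
| $3,000 | about 14–15% | about 76% |

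Hand check for $3,000: SE = √((13,000² + 10,000²)/30) = $2,994, and Φ(−3,000/2,994) = 16%, close to the simulated value.

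**4. Counts and totals against means and proportions**

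Assumed $13,000 v $10,000 per person, remission 46% v 4%. Per participant: 3,000/0.42 = $7,143. With group totals and counts:

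- 30 v 30: (390,000 − 300,000)/(13.8 − 1.2) = $7,143, identical.
- 27 v 24, which is 10% and 20% loss, the two rates in Section 9.2: (351,000 − 240,000)/(12.42 − 0.96) = $9,686, or 36% higher.
- 60 v 30, if the HIWL arms were pooled: (780,000 − 300,000)/(27.6 − 1.2) = $18,182. At $9,000 v $10,000 the same formula gives (540,000 − 300,000)/26.4 = +$9,091, where the per-participant ratio is −1,000/0.42 = −$2,381.

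**5. DSME cost, if it were omitted**

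Each $1,000 left out adds 1,000/0.42 = $2,381 per remission at 46% v 4%, or 1,000/0.33 = $3,030 at 36% v 3%. The resources exist: an initial class or appointment and at least quarterly visits (Section 6.1.1), weekly clinician review of glucose logs (6.5.1) and a connected glucometer (8.2).

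**The case against.** Much can be said for the plan as written.

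- *Group size.* A reader might infer that the analysis divides costs across unequal groups. The documents do not say so. Planned arms are 30 each, Section 9.4.1 speaks of one intervention arm, and Section 8.1 costs the two HIWL arms separately, which fits pairwise comparisons. Total cost in 8.1 is also a category (intervention plus utilization), not necessarily a sum over patients. The combined HIWL contrast belongs to the hypotheses in Section 9.1. What stands is that the comparison is not named, and that groups can become unequal through attrition, through the analysis set in 9.3 (randomized and treated), or through pooling.
- *The switch.* It is announced in advance and hides little. Measure (a) is Δ intervention cost/Δ remissions and measure (b) is −Δ utilization cost/Δ remissions, so (a) − (b) is the ICER. The phrase may also refer to the study's general context, so that both measures are always reported. The data-dependent reading is the more natural one, but the wording is ambiguous.
- *Intervals.* A reader might infer that the bootstrap intervals will mislead. That is not shown for remission. Even percentile intervals, a type the plan does not name, covered about 92–95% in the simulation. More than 2.5% of resamples had a remission difference at or below zero in about 1% of trials at 46% v 4% and 4–6% at 36% v 3%. Only at a weaker assumed effect, 24% v 4%, did this reach 36–37%.
- *DSME cost.* A reader might infer that it counts nowhere. Section 8.1 speaks of intervention cost being higher than in the control arm, and measure (a) is an additional cost; both imply a control cost. The list is incomplete rather than clearly exclusive.
- *A1c and QALY.* The sentence begins by pointing back to the incremental measures, and could mean each active arm against control. The literal wording says otherwise, and this part of the concern stands most firmly.

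**Conclusion.** The point holds in a limited form. As worded, the A1c and QALY ratios are per-arm averages that do not serve the comparative aim. They can miss the incremental ratio in either direction, and in a 30-person arm with an assumed EQ-5D change SD of 0.15 between 3% and 50% of bootstrap denominators are non-positive for mean changes from 0.05 down to 0. The remission measure appears to depend on the observed sign of the cost difference, which under the assumed cost distribution is negative in about 36% of trials when the true difference is +$1,000. The count-based ICER is sound at 30 v 30 and at risk only if totals are used with unequal groups; the sizes shown for that case depend on invented dollar values and are not properties of this plan. The DSME cost list needs completing. Because the objective is exploratory, this is a recommended repair to the analysis text and does not threaten the trial's main conclusions.

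**What to change.** In Section 9.4.1:

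1. Name the comparison: each HIWL arm against DSME, or the pooled HIWL arms against DSME.
2. Replace the per-arm A1c and QALY averages with incremental estimates against DSME.
3. Define the ICER with mean cost per participant and the proportion in remission.
4. Report incremental intervention, utilization and total cost per participant, and the incremental effect, each with a bootstrap confidence interval, whatever the sign. Add a joint summary such as the bootstrap cost-effectiveness plane. Net benefit over a stated willingness-to-pay range is optional, since the documents give no such values.

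In Section 8.1 (Cost data), state that DSME visits, educator time and supplied devices are costed on the same Medicare and micro-costing basis as the HIWL items.

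The cost is revised wording, a little more standard analysis code, and recording of DSME staff time while the trial runs.

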10 SUPPORTING DOCUMENTATION AND OPERATIONAL CONSIDERATIONS

10.1 REGULATORY, ETHICAL, AND STUDY OVERSIGHT CONSIDERATIONS

10.1.1 INFORMED CONSENT PROCESS

Written informed consent will be obtained from all participants during the baseline study visit.

10.1.1.1 CONSENT PROCEDURES AND DOCUMENTATION

A trained staff member or investigator will give an overview of the study, describe the intervention components and data collection requirements, and encourage potential participants to ask questions. All potential participants will be informed of the study design and interventions, the risks and benefits of participation, their rights and responsibilities as research participants, and alternatives to participation. They will also be informed that participation is voluntary and that they can withdraw from the study if their initial or on-going experience makes it oppressive, burdensome, or otherwise uncomfortable. Potential participants will be asked to read the informed consent form and to ask questions. The form will be written in simple, easy-to-understand language. As a part of the consent process, study staff will be required to review all key aspects of the study verbally and will be provided with a structured checklist for this purpose. A copy of the signed and dated consent form will be given to participants, and the original document will be placed in the participants' individual study files, which will be stored in a secure location at the clinical site.

10.1.2 CONFIDENTIALITY AND PRIVACY

Confidentiality will be protected by collecting only information needed to assess study outcomes, minimizing to the fullest extent possible the collection of any information that could directly identify subjects, and maintaining all study information in a secure manner. To help ensure subject privacy and confidentiality, only a unique study identifier will appear on the data collection form. Any collected patient identifying information corresponding to the unique study identifier will be maintained on a linkage file, store separately from the data. The linkage file will be kept secure, with access limited to designated study personnel. Following data collection subject identifying information will be destroyed by deleting any data files three years after study closure, consistent with data validation and study design, producing an anonymous analytical data set. Data access will be limited to study staff. Data and records will be kept locked and secured, with any computer data password protected. No reference to any individual participant will appear in reports, presentations, or publications that may arise from the study.

10.1.3 FUTURE USE OF STORED SPECIMENS AND DATA

Participants who provide consent for storage of blood samples will have a sample of blood stored with a unique identifier that will not include any identifiable information. The unique identifier will be a randomly assigned number and only the principal investigator will have access to the code that links the unique identifier to the study participant. In the case that future researchers need to know more details

about the study participants' health, only those participants who consented to being contacted in the future for inclusion in additional research will be contacted.

10.1.5 KEY ROLES AND STUDY GOVERNANCE

Principal Investigator	Medical Monitor
Study coordinator	Maintenance of regulatory documents; reporting to IRB
Investigator team	Review of data, outcomes, and safety events
Biostatistician	Analysis

10.1.5 SAFETY OVERSIGHT

The principal investigator will be responsible for the overall monitoring of the data and safety of study participants. The principal investigator will be assisted by other members of the study staff.

10.1.6 CLINICAL MONITORING

The clinical care teams for each treatment group will be responsible for monitoring the clinical health of the participants as it pertains to the conduct of this protocol.

10.2 ADDITIONAL CONSIDERATIONS

10.3 ABBREVIATIONS AND SPECIAL TERMS

AE	Adverse Event
ANCOVA	Analysis of Covariance
CFR	Code of Federal Regulations
CLIA	Clinical Laboratory Improvement Amendments
CMP	Clinical Monitoring Plan
COC	Certificate of Confidentiality
CONSORT	Consolidated Standards of Reporting Trials
CRF	Case Report Form
DCC	Data Coordinating Center
DHHS	Department of Health and Human Services
DSMB	Data Safety Monitoring Board
DRE	Disease-Related Event

EC	Ethics Committee
eCRF	Electronic Case Report Forms
FDA	Food and Drug Administration
FDAAA	Food and Drug Administration Amendments Act of 2007
FFR	Federal Financial Report
GCP	Good Clinical Practice
GLP	Good Laboratory Practices
GMP	Good Manufacturing Practices
GWAS	Genome-Wide Association Studies
HIPAA	Health Insurance Portability and Accountability Act
IB	Investigator's Brochure
ICH	International Council on Harmonisation
ICMJE	International Committee of Medical Journal Editors
IDE	Investigational Device Exemption
IND	Investigational New Drug Application
IRB	Institutional Review Board
ISM	Independent Safety Monitor
ITT	Intention-To-Treat
LSMEANS	Least-squares Means
MedDRA	Medical Dictionary for Regulatory Activities
MOP	Manual of Procedures
NCT	National Clinical Trial
NIH	National Institutes of Health
NIH IC	NIH Institute or Center
OHRP	Office for Human Research Protections
PI	Principal Investigator
QA	Quality Assurance
QC	Quality Control
SAE	Serious Adverse Event
SAP	Statistical Analysis Plan
SMC	Safety Monitoring Committee
SOA	Schedule of Activities
SOC	System Organ Class
SOP	Standard Operating Procedure
UP	Unanticipated Problem
US	United States

10.4 PROTOCOL AMENDMENT HISTORY

Version	Date	Description of Change	Brief Rationale
---------	------	-----------------------	-----------------

[illegible]

